### Sample size

Table 5 presents sample size estimates for national 2001-2010 Medicaid data based on our preliminary analyses. For example, we expect that the following treatments with corresponding numbers will be options for the depression symptom subgroup: second antipsychotic (n = 2,192), mood stabilizer (n = 1,296), antidepressant (n = 4,646), and benzodiazepine (n = 1,199). We will then, for example, compare 2,192 patient episodes with a second antipsychotic to 2,192 propensity-score matched patient episodes that were treated with an antidepressant. The 1:1 matching method uses a nearest neighbor algorithm. As recommended for observational studies, we will use a caliper width of 0.2 of the standard deviation of the logit of the propensity score to ensure appropriate matching.

Our power analysis is based on two-sided ( $\alpha = .05$ ) tests for differences in proportions between treatment groups, which depend upon the sample size of each group and the probability of the outcome. To demonstrate power, we conservatively use the expected number of distinct patients rather than episodes (distinct patients equal approximately 70% of the episodes in Table 5). Final statistical analyses of individual episodes will have greater power (i.e., be able to detect even smaller percent differences) and will incorporate random effects to account for patients who contribute more than one episode.

Table 5: Estimated sample sizes of selected schizophrenia treatment episodes (2001-2010)

	Uncomplicated Schizophrenia	Schizoaffective Disorder	Depression	Mania	Anxiety
Second Antipsychotic	27,005	6,393	2,192	1,580	611
Mood Stabilizer	9,954	4,734	1,296	2,107	NA
Antidepressant	25,061	9,692	4,646	NA	1,110
Benzodiazepine	12,248	3,681	1,199	840	1,099

We demonstrate the smallest detectable differences in proportions with >80% power for three examples. For example, in the depression group, 1534 distinct patients per group (70% of 2,192) distinct patients per group (antidepressant vs. second antipsychotic) will provide at least 80% power to detect a difference of 5.0% in the rate of hospital admission in 1 year of follow-up. Also within the depression group, the smallest treatment group (839 distinct patients of 1,199 initiating episodes of benzodiazepines), will provide at least 80% power to detect differences of 6.8% between the reference and the comparator group. In the smallest group overall (611 episodes in anxiety patients starting mood stabilizers), there is still >80% power to detect differences as small as 10.0% in their outcomes compared to those with anxiety in the comparator group. Because of the larger sample sizes, all comparisons in the uncomplicated schizophrenia and schizoaffective disorder groups will have power much greater than 80% to detect a 4% difference in proportions.

These large sample sizes permit identification of statistically significant differences of small magnitude, not all of which may have substantial clinical and policy importance. We will work with our patient, clinical, and policy stakeholders to interpret the meaning of the magnitude of observed treatment effects. The ability to detect small differences (Aim 1) will enable detection of clinically meaningful treatment heterogeneity (Aim 2).

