### Data source and cohort identification

The data source will be national (45-state) Medicaid Analytic Extracts data (2001-2010). The cohort will consist of adults who are 18 to 64 years old and diagnosed with schizophrenia who initiate a new psychotropic medication after a period of stable antipsychotic treatment. Individuals who are 65 or older because will be excluded because they also have Medicare and receive pharmacy benefits through Medicare Part D.

Schizophrenia will be defined as  $\geq 2$  outpatient claims or  $\geq 1$  inpatient claim for schizophrenia [ICD-9-CM: 295] during 365 days of consecutive Medicaid enrollment immediately prior to the index date. Stable antipsychotic monotherapy will be defined by filled prescriptions for only one second-generation antipsychotic (excluding clozapine), and no other psychotropics, for  $\geq 90$  days immediately preceding the start of the index medication (t0). After the  $\geq 90$  days of stable treatment with a single second-generation antipsychotic, study patients will have had a change in therapy defined as (1) addition of a second antipsychotic or (2) addition of a different psychotropic drug class (antidepressant, mood stabilizer, or benzodiazepine). To ensure the patients are in active treatment there must be an active supply of antipsychotic medication on t0.

The eligibility criteria select a cohort of individuals that are likely to have schizophrenia, have received antipsychotic monotherapy prior to the index date, and are still experiencing problems for which a new psychotropic medication strategy was initiated. A 1-year period of eligibility prior to follow-up initiation ensures sufficient time to collect service use related covariates to characterize cohort members.

Patients with stable clozapine monotherapy will be excluded because clozapine is largely reserved for the most severely ill patients. Patients who implement more than one change in therapy at the index date (e.g., addition of a mood stabilizer and an antidepressant) will also be excluded.

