## Outcomes of interest

### Primary

The primary effectiveness outcome will be time to psychiatric hospitalization.

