## Follow-up and censoring

Follow-up will begin at the date of new treatment initiation (t0 or index date) and will end after 365 days regardless of changes in pharmacotherapy (intent-to-treat approach). We will also conduct secondary analyses using a 180-day follow-up period and an as-treated specification. In the as-treated approach, follow-up will end at discontinuation of the new treatment ( $>10$  days without drug) or addition of another psychotropic agent (antipsychotic, mood stabilizer, antidepressant, or benzodiazepine). All analyses will be censored at loss of Medicaid (because that is the data source) with one exception—in intent-to-treat mortality analyses, follow-up will not be censored at loss of Medicaid because date of death data comes from the Social Security Master File, not Medicaid.

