### *Propensity score estimation and application*

Propensity score methods involve two steps: estimation of the propensity scores and application of the propensity score. Estimation of the propensity scores involves decisions about which covariates to include in the prediction model of the propensity scores and what form the model should take. We will use expert opinion to select the variables to include in the propensity score. To estimate the propensity scores we will first use logistic regression including all baseline predictors occurring prior to treatment assignment. In addition, we will augment our analysis with another non-parametric method for building the propensity score model such as a generalized boosting algorithm implemented with regression trees. We will assess the sensitivity of our results to the choice of the propensity score model.

For the application of the propensity scores, we will use weighting by the odds to estimate the average treatment effect on the treated sample and weighting by the inverse probability of treatment weights to estimate the average treatment effect in the population.

We will examine the covariate balance using standardized differences in covariate means across the treatment groups after weighting, and address any significant imbalances.

**AIM 2 Heterogeneity of Treatment Effects:** Within the five subgroups, explore whether the comparative effectiveness and safety of alternative treatment strategies varies according to patient age and presence of a substance use disorder.

We will use similar Cox model techniques for the HTE analyses. First we will assess interaction of age and substance use variables with treatment. If such interactions are found, we will then perform analyses examining alternative treatment strategies stratified by age group or substance use.

The rationale for investigating patient age as a moderator of antipsychotic treatment effects follows from evidence that individuals early in the course of psychosis may respond differently to medications than people with more chronic illness. The rationale for investigating comorbid diagnosis of a substance use disorder as a moderator of treatment effects follows from evidence that people diagnosed with schizophrenia and comorbid substance use disorders respond more poorly to antipsychotic medications than those without comorbid substance use disorders.

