### Sensitivity Analyses

We will conduct sensitivity analyses to confirm findings from the primary analyses and to examine their generalizability. In addition to the primary 360-day intention-to-treat analyses we will conduct 180-day intention-to-treat analyses and as-treated analyses. Another sensitivity analysis will examine subgroups of people with depression, anxiety, or mania diagnoses that are listed by more than one provider.

**Quantitative Sensitivity Analyses for Unmeasured Confounders.** Because the observed relative risk is a closed-form function of the balance of confounders among exposure groups, the strength of the confounder, and the prevalence of the confounder, it is possible to estimate the extent of unmeasured and thus unadjusted confounding necessary to fully explain the observed findings, i.e., would move the observed relative risk to statistical insignificance (the null).

To quantify how strong unmeasured confounding would have to be to explain the observed effect sizes among our comparison groups, we will use the array approach to understand how the strength of unmeasured confounders with known associations with our outcomes, such as BMI and risk of diabetes, and the confounder imbalance among study groups might affect the observed relative risk.

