#### AP treatment Initiation year

2002

2003

2004

2005

2006

2007

2008

2009

Diagnostic History, past year	ICD-9-CM Codes*
Depression	293.83, 296.2x, 296.3x, 296.9x, 298.0x, 300.4x, 311.xx
Anxiety	293.84, 300.0x, 300.2x, 300.3x, 308.3x, 309.21, 309.81, 313.0x, 313.2x, 313.89
Bipolar	296.xx (not 296.2x or 296.3x or 296.9x)
Substance use disorder	291.xx, 292.xx, 303.xx, 304.xx
Moderate/severe mental retardation	318.xx
HIV	042, 043, 044, 079.53, V08
Neoplasms	140.xx-239.xx (Exclude people with malignant neoplasms 140.xx-205.xx)
Diabetes	250.xx
Obesity	270.xx
Hyperlipidemia	272.0x-272.4x, 272.7x, 272.9x
White blood cell diseases	288.xx, 289.xx (exclude neutrophil d/o 288.00-288.04, 288.09, 288.1x)
Anemia	280.xx-285.xx
Drug-related dyskinesia	333.85
Hypertension	401.xx-405.xx
Ischemic heart disease	410.xx-414.xx
Pulmonary circulation diseases	415.xx-417.xx
Cardiac dysrhythmias	427.xx
Heart failure	428.xx
Cerebrovascular disease	430.xx-438.xx
Acute bronchitis and bronchiolitis	466.xx
Chronic bronchitis	491.xx
Pneumonia	480.xx-486.xx
Emphysema	492.xx
Asthma	493.xx
Appendicitis	540.xx-543.xx
Noninfectious enteritis and colitis	555.xx-558.xx
Diverticula of intestine	562.xx
Intestinal obstruction	560.xx
Chronic liver disease and cirrhosis	571.xx
Acute & chronic pancreatitis	577.0x, 577.1x
Cholelithiasis	574.xx
Acute kidney failure	584.xx
Chronic kidney failure	585.xx

Kidney infections	590.xx
Cellulitis and abscess	681.xx–682.xx
Osteoarthritis and allied disorders	715.xx
Intervertebral disc disorder	722.xx
Fractures, all sites	800.xx–829.xx
Fracture of neck of femur	820.xx
Poisoning by psychotropic medication	969.xx
Poisonings	960.xx–989.xx
Suicide and self-inflicted injury	E950-959
Intracranial injury	815.xx-854.xx
Severe cardiovascular diseases	401.0x-404.9x, 410.xx-416.xx, 425.xx-437.xx, 440.xx-447.xx
Schizophreniform	295.4x
Schizoaffective	295.7x

---

\* x indicates inclusion of any 5th digit if available for a diagnosis code.

xx indicates inclusion of any 4th and 5th digits if available for a diagnosis code.

Medication history, past year	Drug class
Psychotropic medication	
Antidepressants	SSRI/SNRI/mirtazapine, TCA and heterocyclic compounds, MAOI, trazodone-related antidepressants, bupropion
Mood Stabilizer	lithium, primary anticonvulsant, secondary anticonvulsant
ADHD medication	psychostimulants, alpha-agonists
Anxiolytic/hypnotics	benzodiazepines, GABA agonists, other newer or older anxiolytic/hypnotic

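### Patient random effects are the only provision for repeat episodes, yet they do not match the population-average effect that the weights target, and 365-day windows of one patient can overlap

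*Combined protocol and SAP*

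**What the plan says.** - **Unit of analysis.** The Sample size section bases power on patients but plans the final analyses on episodes, and says they "will incorporate random effects to account for patients who contribute more than one episode". It gives the ratio as "distinct patients equal approximately 70% of the episodes in Table 5".
- **Follow-up.** Under Follow-up and censoring, each episode starts at its index date and "will end after 365 days regardless of changes in pharmacotherapy (intent-to-treat approach"). Sensitivity Analyses confirms which analysis is primary: "In addition to the primary 360-day intention-to-treat analyses" (360 days there, 365 in the other section).
- **Re-entry.** Data source and cohort identification requires at least 90 days of "filled prescriptions for only one second-generation antipsychotic (excluding clozapine), and no other psychotropics" before an index date. Appendix 2 lists antidepressants, mood stabilizers and anxiolytics under "Medication history, past year" as propensity-score variables, so use of a comparator class earlier in the year does not exclude a patient.
- **Outcome.** "The primary effectiveness outcome will be time to psychiatric hospitalization".
- **Target of the weighting.** Propensity score estimation and application plans odds weights for the effect in the treated and "weighting by the inverse probability of treatment weights to estimate the average treatment effect in the population".
- **Not stated.** No rule limits a patient to one episode, bars a new index date inside an open window, or says where a shared admission is counted. The weighted Cox text names no variance method for repeat patients.
- **Conflict.** The Aim 1 paragraph of the Analysis plan also censors when the added drug is stopped or changed. That is the as-treated rule, which the follow-up section makes secondary.

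**The concern.** A 90-day re-entry rule inside a 365-day window lets two episodes of one patient run at the same time. A psychiatric admission in the overlap is then the first event of both, in the same arm or possibly in opposite arms.

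A patient random effect assumes that episodes are independent once the patient's own risk level is given. One admission entered twice breaks that assumption, and the model can only explain it as more heterogeneity between patients. The random effect also changes the quantity estimated. Its hazard ratio compares treatments at a fixed patient risk level, whereas the weights are chosen to estimate an average effect over the population or over the treated. The reported hazard ratio would then not be the one the plan says it targets. The Sample size section itself notes that samples this large make small differences statistically significant, so a shift of a few percent matters.

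**Working it through.** **1. The plan's own power figure.** Inputs from Sample size: 1,534 patients per group (70% of 2,192 episodes), 5.0 points, two-sided alpha 0.05. No base rate is given, so the worst case is 47.5% against 52.5%.

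Power = Φ[(d − 1.96 × SE0) / SE1], with SE0 = √(0.5/1534) = 0.01805 and SE1 = √(0.49875/1534) = 0.01803. This gives Φ[(0.0500 − 0.0354)/0.0180] = Φ(0.81) = 79.1%. At 30% against 35% it is 84.1%, and at 20% against 25% it is 91.3%. The second example (839 per group, 6.8 points) gives 79.6% at worst. The stated figures are reproduced within rounding.

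Using all 2,192 episodes, with 1/0.7 = 1.43 episodes per patient and design effect 1 + 0.43ρ, power is 90.6%, 88.9%, 85.2% and 79.1% for ρ = 0.05, 0.2, 0.5 and 1 (assumed range).

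**2. Can windows overlap?** If the first added drug lasts d days, the second index date can fall on day d + 90. The 365-day windows then overlap by up to 365 − (d + 90) = 275 − d days.

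| d | earliest second index day | maximum overlap, 365-day window | maximum overlap, 180-day window |
|---|---|---|---|
| 30 | 120 | 245 | 60 |
| 90 | 180 | 185 | 0 |
| 180 | 270 | 95 | 0 |

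**3. How many admissions could be shared?** The document gives no timing of repeats, so every figure here rests on assumptions.
- For a patient with two episodes (frailty variance 1, one-year risk 20% to 50%), 51-62% of first-window admissions are also the second window's first event if the starts are 120 days apart. At 270 days apart it is 15-22%.
- Over a whole cohort (43% of patients with one repeat, so 0.43/1.43 = 30% of episodes; one-year risk about 26%), admissions counted twice were 4-9% of events with repeats within one to two years. They fell to about 0.9% with repeats spread over days 100-2920.

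**4. Conditional against marginal hazard ratio.** With gamma frailty variance θ and one-year risk r, H = ((1 − r)^(−θ) − 1)/θ, and the marginal hazard ratio at one year is HR(1 + θH)/(1 + θ·HR·H). For r = 0.30, θ = 1 and conditional HR 0.80: H = 0.4286, and 0.80 × 1.4286/1.3429 = 0.851. As a ratio of cumulative hazards over the year it is ln(1.3429)/ln(1.4286) = 0.827. For θ = 0.25, 0.5 and 2 the one-year values are 0.814, 0.827 and 0.891.

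**5. The planned type of model.** A gamma-frailty exponential model was fitted to simulated cohorts: 3,000 patients, 43% with one repeat, random allocation, no weights, conditional HR 0.80. Without overlap it recovered a frailty variance of about 1.0 and HR 0.80. With repeats within one to two years, the estimated variance rose to about 1.5-2.4 (true value 1) or 1.0-1.8 (true value 0.5) across runs. Hazard ratios at true variance 1, repeats on days 100-365:

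| repeats | frailty | marginal, all episodes | marginal, first episode | frailty / first |
|---|---|---|---|---|
| opposite arm | 0.81 | 0.85 | 0.86 | 0.94 |
| mixed | 0.80 | 0.83 | 0.84 | 0.95 |
| same arm | 0.79 | 0.82 | 0.82 | 0.96 |

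Over all settings (variance 0.5-1, repeats within one to two years) the frailty hazard ratio was about 3-6% further from the null than the first-episode marginal one.

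**6. Standard errors.** In one set of runs (Monte Carlo error about 4%), model SE over empirical SE for the frailty fit was 1.12, 0.98 and 0.98 (opposite, half, same arm; days 100-365) and 0.99, 1.01 and 1.00 (days 100-730). Across checks, the excess was about 10-17% only when every repeat was cross-arm within a year. Patient-clustered sandwich SEs for the marginal estimate were 0.97-1.01 of empirical.

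**The case against.** Most of the opposing case is sound, and it limits the point.

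- **A reader might infer that the planned standard errors are wrong.** Errors of 16% too large or 12% too small, with coverage down to 91.5%, arise only when clustering is ignored, and the plan does not propose that. With the random effect, standard errors were close to right except in the extreme cross-arm case, where they were conservative.
- **A reader might infer that a shared admission is a counting error that biases the result.** Under intent-to-treat, an admission after two starts belongs to both windows. Marginal all-episode and first-episode hazard ratios differed by 2% or less. In the cross-arm case, part of the gap between the frailty and first-episode hazard ratios is dilution by the later start, which belongs to the intent-to-treat effect.
- **A reader might infer that repeats often fall in opposite arms.** Nothing supports this. The 70% ratio is applied cell by cell (1,534 of 2,192; 839 of 1,199), which is compatible with repeats inside one arm. Sharing also requires both episodes to meet the same subgroup's 30-day, more-than-one-provider diagnosis rule, with no admission between the two starts.
- **Overlap may be rare.** Appendix 2 lists initiation years 2002-2009, and repeats spread over that span would share few events.
- **The Aim 1 censoring rule would remove overlap.** That is true, but it conflicts with the rule named primary.
- **The random-effects sentence sits beside the matching text, not the weighted Cox text.** That is also true. But it is the only provision given, and it is said to apply to the final analyses.

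What remains is the mismatch of estimand, which does not depend on overlap, and the distorted frailty variance, which does.

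**Conclusion.** The point holds in a limited form. Under the 365-day intent-to-treat rule and the 90-day re-entry rule, windows of one patient can overlap, and one admission may be the first event of two episodes in the same subgroup. The only stated provision gives a patient-conditional hazard ratio, whereas the weights target population-average effects.

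The likely size is a hazard ratio about 3-6% further from the null. This rests on an assumed frailty variance of 0.5 to 1, repeats within one to two years, random allocation and no weights. A smaller frailty variance narrows the conditional-marginal gap, and later repeats reduce event sharing.

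The document does not support a claim of invalid standard errors, nor one of overstated power. The power examples already use distinct patients and are reproduced.

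**What to change.** 1. Reconcile the Aim 1 censoring sentence, and the 360-day figure, with the 365-day intent-to-treat rule. Overlap arises only under intent-to-treat.
2. State the episode rule: whether all qualifying episodes enter, and whether a new index date may fall inside an open window.
3. In the weighted Cox models, replace random effects with a patient-clustered robust (sandwich) variance, or a bootstrap that resamples patients. Either keeps the marginal target and lets shared events within a patient add or cancel in the variance as they should.
4. Report the primary outcome on each patient's first qualifying episode as a sensitivity analysis, and tabulate the number of overlapping episodes and shared admissions by subgroup and by same or opposite arm.

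The cost is SAP wording and one extra run. First-episode intervals will be wider. A patient with episodes in two arms counts in both cells of the power calculation but would be kept in only one, so some cells could fall below 1,534 or 839 if many repeats are cross-arm.

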## Goal

More than half of individuals diagnosed with schizophrenia have an incomplete response to a prescribed antipsychotic medication. In spite of the high proportion of patients who experience an incomplete response, little is known about the comparative effectiveness of treatment options that are commonly used in this situation. The proposed research question “For patients with schizophrenia who have persistent, emergent or recurrent psychiatric symptoms in spite of antipsychotic treatment, what are the medication treatment options and what are their comparative benefits and risks?” thus has considerable public health importance is relevant to a large proportion of the approximately 3 million individuals with schizophrenia in the U.S. specifically, the project seeks to achieve the following aims:

1. Within five clinically important schizophrenia subgroups, compare the effectiveness and safety of alternative medication strategies beyond antipsychotic monotherapy.
2. Within the five subgroups, explore whether the comparative effectiveness and safety of alternative treatment strategies varies according to patient age and presence of a substance use disorder.
3. Conduct instrumental variable and sensitivity analyses to examine the robustness of the treatment effectiveness results that are based on propensity score methods.

The project will yield unbiased, generalizable, and patient-centered information on the comparative effectiveness and safety of alternative medication strategies for patients with schizophrenia who have an incomplete response to

standard antipsychotic monotherapy. New information will be generated regarding the comparative effectiveness and safety of commonly used but poorly understood second-line medication treatment strategies. We will compare the effectiveness of these medication treatment strategies for schizophrenia in five subgroups based on presenting symptoms and syndromes that lead to initiation of a new psychotropic strategy: 1) schizoaffective, 2) depressive, 3) anxiety, 4) manic, and 5) uncomplicated schizophrenia.

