### Comparators

Pharmacological treatment options for patients with schizophrenia who are nonresponsive to antipsychotic monotherapy will include (1) initiation of a second antipsychotic, (2) initiation of an antidepressant, (3) initiation of a mood stabilizer and (4) initiation of a benzodiazepine.

Within each clinical subgroup, treatment options may be refined by exclusions at the drug class or individual agent level. For example, antidepressants are generally not considered treatment alternatives in patients presenting with mania, but could reasonably be considered for patients in the remaining four schizophrenia subgroups: depression, anxiety, schizoaffective disorder, and uncomplicated schizophrenia. Unless it is not considered a reasonable treatment option for a specific subgroup, initiation of a new antipsychotic will serve as the reference category because it is a frequently recommended approach to improving treatment response and is a common treatment strategy across all of the clinical subgroups under study. A survey on the prescribing behaviors of clinicians who prescribe psychotropic medications for individuals with schizophrenia will inform these choices.

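### Aim 2 power is inferred from main-effect power, but the smallest detectable interaction is at least about twice the detectable main effect

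*Combined protocol and SAP*

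**What the plan says.** The Sample size section bases power on two-sided (alpha 0.05) "tests for differences in proportions between treatment groups, which depend upon the sample size of each group and the probability of the outcome". It gives no value for that probability. It counts distinct patients, about 70% of the Table 5 episodes, and adds that "Final statistical analyses of individual episodes will have greater power".

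Three detectable differences are given at 80% power or more: 5.0 points (depression, 1,534 per group), 6.8 points (depression/benzodiazepine, 839) and 10.0 points (anxiety, from 611 episodes). All comparisons in the uncomplicated and schizoaffective subgroups are said to have power well above 80% for 4 points. The statement on Aim 2 follows: "The ability to detect small differences (Aim 1) will enable detection of clinically meaningful treatment heterogeneity (Aim 2".

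Under Goal, Aim 2 is to "explore whether the comparative effectiveness and safety of alternative treatment strategies varies according to patient age and presence of a substance use disorder". The Aim 2 paragraph, under Propensity score estimation and application, says "We will use similar Cox model techniques for the HTE analyses". Interactions of treatment with age and substance use are assessed first, and then: "If such interactions are found, we will then perform analyses examining alternative treatment strategies stratified by age group or substance use".

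**The concern.** Precision for a difference between two arms does not carry over to a difference between two such differences, each estimated in only part of the sample. The plan has no interaction calculation, no modifier prevalence, no age coding for the interaction test and no size for a clinically meaningful interaction. The power statement for Aim 2 therefore rests on Aim 1 alone.

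What is at stake is how a null result is read. The stratified analyses run only if an interaction is found, there is no rule for what counts as found, and nothing says how a non-finding will be interpreted. A reader who trusts the power statement could take a non-significant interaction as evidence that treatments compare equally across age or substance use, when an interaction as large as the stated main effects could have been missed.

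**Working it through.** **Inputs from the documents.** Alpha 0.05 two-sided, 80% power, 1:1 matching, distinct patients = 70% of Table 5. Per arm: depression/antidepressant 1,534 (from 2,192); depression/benzodiazepine 839 (1,199); anxiety 427 (611); smallest uncomplicated contrast 6,967 (9,954).

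**Assumptions, because the documents give neither.** Event rate p of 20-50%; share f of patients with the modifier, 50% down to 25%.

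**1. The plan's own figures.** Detectable main effect = 2.80 × sqrt(2p(1−p)/n), with 2.80 = 1.96 + 0.84.
- n = 1,534: 5.06 points at p = 50%, 4.96 at 40% (stated 5.0).
- n = 839: 6.84 at 50%, 6.70 at 40% (stated 6.8).
- n = 427: 9.6 at 50%. Power for 10.0 points is about 83-84%, as claimed.

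The stated figures therefore reproduce at an event rate of about 40-50%.

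**2. Main effect to interaction.** With similar variance and the same split in both arms, the standard error of the difference between two stratum-specific effects is that of the main effect multiplied by 1/sqrt(f(1−f)). This is 2.00 at f = 50% (the minimum), 2.31 at 25%, 2.50 at 20% and 3.33 at 10%. An interaction equal in size to an exactly 80%-powered main effect has power Φ(2.80/2.00 − 1.96) = 28.8% at 50/50 and Φ(2.80/2.31 − 1.96) = 22.8% at 25/75.

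**3. Detectable interaction at 80% power**, matched distinct patients, percentage points. The low end is p = 20%, f = 50%; the high end is p = 50%, f = 25%.

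| Contrast with second antipsychotic | n per arm | Stated main effect | Detectable interaction |
|---|---|---|---|
| Depression/antidepressant | 1,534 | 5.0 | 8.1-11.7 |
| Depression/benzodiazepine | 839 | 6.8 | 10.9-15.8 |
| Anxiety | 427 | 10.0 | 15.3-22.1 |
| Uncomplicated, smallest | 6,967 | 4 | 3.8-5.5 |

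First row, high end: 5.06 × 2.31 = 11.7. In the last row, a 4-point interaction has 66% (50/50) to 53% (25/75) power at p = 50%, and 84% to 72% at p = 20%.

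**4. Dependence on event rate and unit.** Power for an interaction equal to the stated 5.0, 6.8 or 10.0 points:

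| Event rate | Matched distinct patients | All episodes, taken as independent (upper bound) |
|---|---|---|
| 40-50% | 22-32% | 37-53% |
| 20% | 32-45% | 54-70% |
| 10% | 52-68% | 78-91% |

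It reaches 80% once the rate falls to about 5-7% (matched patients) or 10-15% (all episodes).

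**5. Cox scale.** Aim 2 is planned with Cox models, where a lower rate means fewer events. The detectable ratio of hazard ratios is exp(2.80 × sqrt((1/d1 + 1/d2)/(f(1−f)))), with d = p × n events per arm and no censoring. For depression/antidepressant, matched patients, it is 1.33-1.39 at p = 50% (d = 767) and 1.90-2.09 at p = 10% (d = 153). A low rate helps on the risk-difference scale and hurts on this one, so rate and scale both have to be stated.

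**6. Two minor checks.**
- *Label.* The text reads "In the smallest group overall (611 episodes in anxiety patients starting mood stabilizers". Table 5 shows NA for mood stabilizers in anxiety and lists 611 under second antipsychotic. By default that is the reference arm (Comparators: "initiation of a new antipsychotic will serve as the reference category").
- *The 4-point claim.* Schizoaffective/benzodiazepine has 3,681 × 0.70 = 2,577 patients per arm. For 50% versus 46%: 0.04/sqrt((0.25 + 0.2484)/2,577) − 1.96 = 0.92, power 82.0%. From a 40% rate it is 82.9% (versus 44%) or 84.1% (versus 36%). With 3,681 matched episodes per arm it is 93.0%.

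**The case against.** Aim 2 is worded as exploration, for which a formal interaction power calculation is optional. The power statement promises to detect heterogeneity that matters clinically, not interactions equal to the Aim 1 detectable differences. That benchmark is mine, and without a threshold in the plan the claim is unsupported rather than refuted. The factor of 2.0-2.3 needs a split between 25/75 and 50/50 and similar variance across strata. The plan itself expects poorer antipsychotic response with substance use disorders, so equal event rates are uncertain. Final analyses use episodes, and the analysis section applies weighting, so matched distinct patients are a conservative basis. All of this stands, and it is why the factor is given conditionally. It does not supply the missing calculation, and an exploratory aim still needs a correct account of what a null result means.

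Three stronger readings are tempting and are not supported:
- That Aim 2 cannot reach 80% power. It can at low event rates, on the risk-difference scale.
- That the problem stops at uncomplicated schizophrenia, so that a null result there shows homogeneity. A 4-point interaction there has only 53-66% power at a 50% rate with matched patients.
- That the Aim 1 figures are wrong. They reproduce, and the 611 slip changes no number. The 4-point claim falls short in one contrast only, at an inferred 40-50% rate with matched distinct patients. The other contrasts with the reference arm in those two subgroups have 90% or more on the same basis at a 50% rate.

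**Conclusion.** The point holds as an unsupported inference with consequences for interpretation; it is not a design failure. For a two-level modifier with similar variance across strata, the detectable interaction is at least about twice the detectable main effect, and an interaction the size of an exactly 80%-powered main effect has about 23-29% power at splits from 25/75 to 50/50. The percentage-point ranges depend on the assumed event rate and modifier split, and on matched distinct patients as the unit. The factor itself does not depend on the event rate, but it does depend on the split and on how age is coded. The wrong label and the missing event rate are minor. The figures for the 4-point claim call for a qualification only if the rate used was about 40-50%.

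**What to change.** - Replace the Aim 2 power statement with detectable interactions for each subgroup, under a stated event rate, modifier split, age coding, effect scale and analysis unit.
- In the Aim 2 analysis text, commit to reporting interaction estimates with confidence intervals whether or not the test is significant. State that a non-significant interaction in any subgroup, including uncomplicated schizophrenia, is not by itself evidence of homogeneity.
- Relabel the 611 anxiety episodes as second antipsychotic, to match Table 5. The 10.0-point claim stays.
- State the event rate behind the power figures. If it is about 40-50%, qualify the 4-point claim for schizoaffective/benzodiazepine: about 82-84% with matched distinct patients, about 93% with matched episodes.

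The cost is recomputation and rewording, with no new data and no change of design. The Aim 2 power statement will read less favourably.
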